4.7. Resistance Determinations

Inclusion of subjects for resistance analysis will be based on the availability of post-baseline genotypic/phenotypic data also described below.

4.7.1. Genotype

HIV-1 PR/RT genotype will be assessed by the GenoSureMG™ assay. Genotypes were requested on eligible samples with a viral load ≥ 400 copies/mL. Results will be shown per PR and RT and time point and will be generated in individual listings. Name and date of mutation lists will be indicated.

The analysis aims to characterize the frequency of post-baseline PR and RT resistance mutations in all subjects with genotype data and in subjects with virologic rebound having genotype data.

A tabulation per treatment group will present the number of patients with a specific mutation or number of patients with at least one PR or RT mutation belonging to a specific mutation list (see below). The analysis assumes a worst case scenario in case of multiple post-baseline sequencing results: if any of a patient's samples shows a mutation, the patient is assumed to have this mutation, even if other samples show wild-type virus.

All analyses will be conducted on the Efficacy ITT population, unless specified otherwise.

Protease mutations

- IAS-USA² Primary PI mutations (n=23)
D30N, V32I, M46I/L, I47A/V, G48V, I50L/V, I54L/M, Q58E, T74P, L76V, V82A/F/L/S/T, N83D, I84V, N88S, L90M
- IAS-USA² Secondary PI mutations (n=52)
L10C/F/I/R/V, V11I, G16E, K20I/M/R/T/V, L24I, L33I/F/V, E34Q, M36I/L/V, K43T, F53L/Y, I54A/S/T/V, D60E, I62V, L63P, I64L/M/V, H69K/R, A71I/L/T/V, G73A/C/S/T, V77I, V82I, I85V, N88D, L89I/M/V, I93L/M
- IAS-USA² DRV resistance-associated mutations (n=11)
V11I, V32I, L33F, I47V, I50V, I54L/M, T74P, L76V, I84V, L89V

RT mutations

- IAS-USA² NRTI resistance-associated mutations (n=22)
M41L, A62V, K65R/E/N, D67N, 69ins, K70E/R, L74V, V75I, F77L, Y115F, F116Y, Q151M, M184I/V, L210W, T215F/Y, K219E/Q

- IAS-USA² NNRTI resistance-associated mutations (n=34)
V90I, A98G, L100I, K101E/H/P, K103N/S, V106A/I/M, V108I, E138A/G/K/Q/R, V179D/F/L/T, Y181C/I/V, Y188C/H/L, G190A/S, H221Y, P225H, F227C, M230I/L
- IAS-USA² Thymidine Analogue Mutations (TAMs) (n=8)
M41L, D67N, K70R, L210W, T215Y/F, K219Q/E
- IAS-USA² TFV resistance-associated mutations
K65R/E/N, K70E
- IAS-USA² FTC resistance-associated mutations
K65R/E/N, M184I/V

4.7.2. Phenotype

Predicted phenotype based GenoSureMG™ and in-vitro phenotype data, if applicable, based on PhenoSense™ HIV assay, will be presented in individual patient listings per drug and time point. Fold change (FC) in 50% effective concentration (EC50) of ARVs versus wild-type HIV-1 virus will be included in individual listings per drug and time point.

PhenoSense™ could additionally be requested to determine the phenotypic drug susceptibility of the virus if resistance-associated mutations to the study drugs were observed. Using the fold change (FC), each drug will be categorized into sensitive/partially sensitive/resistant based on cut-off values.

Number and percentage of genotypic/phenotypic susceptibility (i.e., sensitivity) will be tabulated (numbers and proportions) per class and drug.

When one cut-off value is available, a drug is considered

- Sensitive if the FC is below or equal to the clinical cut-off (CCO) when available or below or equal to the biological cut-off (BCO) otherwise;
- Resistant if the FC is above the clinical or biological cut-off.

When two cut-off values are available, a drug is considered

- Sensitive if the FC is below or equal to the lower cut-off;
- Partially sensitive if the FC is above the lower cut-off and below or equal to the higher cut-off;
- Resistant if the FC is above the higher cut-off.

BCOs and CCOs for the PhenoSense® GT Phenotyping Assay

Class	Drug	Generic name	Cut-off PhenoSense GT™ (V7045/V7145)
NRTI	AZT	Zidovudine	1.9
	3TC	Lamivudine	3.5
	ddI	Didanosine	1.3 – 2.2
	d4T	Stavudine	1.7
	ABC	Abacavir	4.5 – 6.5
	FTC	Emtricitabine	3.5
	TDF	Tenofovir	1.4 – 4.0
NNRTI	NVP	Nevirapine	4.5

	DLV	Delavirdine	6.2
	EFV	Efavirenz	3.0
	ETR	Etravirine	2.9 – 10.0
	RLP	Rilpivirine	2.0
PI	ATV	Atazanavir	2.2
	ATV/rtv	Boosted Atazanavir	5.2
	DRV/rtv	Boosted Darunavir	10.0 – 90.0
	APV/rtv or fAPV/rtv	Boosted Amprenavir or fosamprenavir	4.0 – 11.0
	IDV/rtv	Boosted Indinavir	10.0
	LPV/rtv	Boosted Lopinavir (Kaletra)	9.0 – 55.0
	NFV	Nelfinavir	3.6
	RTV	Ritonavir	2.5
	SQV/rtv	Boosted Saquinavir	2.3 – 12.0
	TPV/rtv	Boosted Tipranavir	2.0 – 8.0

Clinical cut-offs are shown in bold; cutoffs are based on the PhenosenseGT algorithm version 13

5. SAFETY

For initial switchers, comparative treatment phase (study baseline to Week 48), extended treatment phase (Week 48 to Week 96) as well as combination of both phases (study baseline to Week 96) will be presented in the tables. For late switchers, comparative treatment phase (study baseline up to the switch) and extended treatment phase (from the switch to Week 96) will be presented.

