2. GENERAL ANALYSIS DEFINITIONS

2.4. Treatment Arms

Following notations for the treatment arms in extension will be used:

- **Initial switch to D/C/F/TAF:** subjects who received D/C/F/TAF treatment at baseline of the treatment phase (initial switchers)
- **Late switch to D/C/F/TAF:** subjects who continued on their bPI treatment for 52 weeks and who switched to D/C/F/TAF treatment in the extension (late switchers)

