2.5. Visit Windows

2.5.1. Trial Phases

Phases will be constructed for each subject as follows for adverse events, concomitant therapies, and for the determination of the worst-case/toxicity/change in the cross-tabulations.

Trial phase	Start date	End date
Screening	Minimum of Date of signing the informed consent and Date of the screening visit	1 day before start of treatment
Comparative Treatment Phase	Date of the first intake (after randomization)	
For initial D/C/F/TAF subjects, in order of priority:
 
 - Week 48 visit date; if missing then - Projected Week 48 visit date, where projected Week 48 visit date = baseline visit date + (7 *48) 
For late switchers: Date of first D/C/F/TAF intake-1 day
 
In case of withdrawal use:
 
 - Minimum(last intake date of study drug, study withdrawal date) + 2 days
Extended Treatment Phase (Extension)	Last Date of Comparative Treatment Phase +1 day	
 - Week 96 visit date; if missing then - Projected Week 96 visit date, where projected Week 96 visit date = baseline visit date + (7 *96) 
In case of withdrawal use:
 
 - Minimum (last intake date of study drug, study withdrawal date) + 2 days
Follow-up	End of last treatment phase +1 day	Trial termination date for all groups (date of last contact)

Data up to each subject's Week 96 visit are in scope for this analysis, DXA data (DP domain) up to Week 96 visit+28 days, and if applicable, any (confirmatory) viral load or genotype/phenotype results immediately subsequent to Week 96 (up to 6 weeks).

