2.6. Analysis Sets

2.6.1. Intent-to-Treat Analysis Set

The intent-to-treat (ITT) analysis set includes all the subjects who were randomized and received at least 1 dose of treatment subsequent to randomization in the study. Efficacy data up to the last dose date of the treatment are included. The safety analysis (including all data collected at the 30-day FU visit) is also performed on this analysis set.

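### In the descriptive Week 96 safety tables, the comparative-phase adverse event columns run to Week 48 for D/C/F/TAF but to about Week 52 for control, with crude incidences only

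*SAP*

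**What the plan says.** SAP 2.5.1 builds the trial phases "for adverse events, concomitant therapies, and for the determination of the worst-case/toxicity/change in the cross-tabulations". For initial D/C/F/TAF subjects the comparative phase ends at the Week 48 visit or, if that is missing, at the baseline visit date plus 7 × 48 days. For late switchers it ends at "Date of first D/C/F/TAF intake-1 day". In both arms a subject who withdraws is cut at "Minimum(last intake date of study drug, study withdrawal date) + 2 days". The extended phase starts at "Last Date of Comparative Treatment Phase +1 day".

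SAP 5 carries the same split into the safety tables. For one arm it reads "For initial switchers, comparative treatment phase (study baseline to Week 48), extended treatment phase (Week 48 to Week 96"; for the other, "For late switchers, comparative treatment phase (study baseline up to the switch". SAP 1.2 and 2.4 place the switch at Week 52, and Protocol 9.1.4 has AEs collected at that visit.

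SAP 5.4.2 specifies AE summaries and incidences by system organ class and preferred term, with no formal testing. It gives no exposure-adjusted rate and no time-to-event analysis of AEs. SAP 3.7 derives subject-years but does not link them to the AE tables. It also leaves unclear whether control exposure before the switch is shown.

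**The concern.** Two columns with the same phase label will be read against each other. Control subjects who reach the switch contribute about four more weeks in which a first event can occur, and a crude percentage does not allow for that. With identical true hazards the control column reads higher, so the tilt favours D/C/F/TAF. It applies to every AE row built on these phases: serious events, deaths due to AE, grade 3 or 4 events, discontinuations, the AE-of-interest groups and fractures. Protocol 11.1.2 frames its AE proportions as through 24, 48 and 96 weeks, and a control column running to about Week 52 is not a 48-week proportion.

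**Working it through.** The plan states no figure on this point, so there is none to reproduce.

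**Inputs from the documents.** D/C/F/TAF window: 48 × 7 = 336 days (SAP 2.5.1). Control window: to the Week 52 switch, 52 × 7 = 364 days (SAP 1.2, 2.4). Planned control n = 367 and D/C/F/TAF n = 734 (SAP 1.2).

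**Assumed.** Constant and equal first-event hazards; 48-week risks p of 5% and 20%; a share d in each arm withdrawing evenly over 48 weeks; a share q of control leaving at about Week 48 without switching. The two extra days in the withdrawal rule are ignored.

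**Time at risk.** With s = 1 − d − q, the control to D/C/F/TAF ratio is (52s + 48q + 24d) / (48(1 − d) + 24d). Extra control subject-years are 367 × s × 28 / 365.25.

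- d = q = 0: 52/48 = 1.083, or +8.3%; 28.1 subject-years
- d = 0.10, q = 0: 49.2/45.6 = 1.079, or +7.9%; 25.3 subject-years
- d = q = 0.10: 48.8/45.6 = 1.070, or +7.0%; 22.5 subject-years

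Moving both end dates by 7 days in opposite directions for every subject puts the gap between 14 days (357/343, +4.1%) and 42 days (371/329, +12.8%).

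**Crude incidence.** Over w weeks it is 1 − (1 − p)^(w/48). With no withdrawal, control at 52 weeks reads:

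- p = 5%: 5.41%, an excess of 0.41 points, or 1.5 of 367 subjects
- p = 20%: 21.47%, an excess of 1.47 points, or 5.4 subjects

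With withdrawal, D/C/F/TAF against control:

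- d = 0.10, q = 0: 4.75% against 5.12%, and 19.04% against 20.36%
- d = q = 0.10: 4.75% against 5.08%, and 19.04% against 20.22%

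The excess is therefore 0.3 to 0.4 points at 5% and 1.2 to 1.5 points at 20%. With no withdrawal, the largest gap at any incidence is about 2.9 points, near 62%.

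**Extended phase.** The order reverses. Late switchers have 96 − 52 = 44 weeks against 48, so a 48-week risk of 20% reads 1 − 0.80^(44/48) = 18.5%.

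**Would dividing by total treatment duration repair it?** Take subjects with an event over total duration, with no withdrawal. The D/C/F/TAF to control rate ratio is (p/48) / (p52/52), where p52 is the 52-week incidence.

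- 20%: crude control to D/C/F/TAF ratio 1.074; D/C/F/TAF rate 0.9% higher
- 50%: crude ratio 1.056; D/C/F/TAF rate 2.6% higher
- 80%: crude ratio 1.031; D/C/F/TAF rate 5.0% higher

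The bias changes direction, and above an incidence of about 70% it exceeds the crude one. If person-time stops at the first event, expected person-time per subject is incidence divided by the hazard. The rate then equals the hazard in both arms whatever the window.

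**The case against.** The strongest reply is that nothing inferential depends on these columns. This SAP covers Week 96 only, tests no hypothesis (SAP 1.3), is descriptive (SAP 4.4.1) and does no AE testing (SAP 5.4.2). It does not call for a between-arm AE contrast. The windows are stated openly. Ending control the day before first D/C/F/TAF intake keeps bPI events with bPI, which is sensible. The effect is also small: with 734 and 367 subjects the standard error of a difference is √(0.05 × 0.95 × (1/734 + 1/367)) = 1.4 points at 5% and, likewise, 2.6 points at 20%. The artefact is roughly a quarter to 60% of one standard error.

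Most of this stands, and it limits the point to a modest one. It does not remove it: the SAP chooses to present the comparative phase again, and without a test the displayed percentages are the result.

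Two stronger readings are tempting, and the documents support neither.

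- A reader might infer that the primary Week 48 safety comparison is biased. That analysis is separate and its SAP is not among the documents, so its AE cut-off cannot be judged.
- A reader might infer that control deaths and discontinuations before the switch are left out, because SAP 2.4 defines late switchers as "subjects who continued on their bPI treatment for 52 weeks and who switched to D/C/F/TAF treatment in the extension (late switchers". But SAP 2.6.1 defines the ITT set as all randomized and treated subjects and says "The safety analysis (including all data collected at the 30-day FU visit) is also performed on this analysis set", and the withdrawal rule in SAP 2.5.1 gives early leavers a phase end. All treated control subjects appear to be meant; the wording needs clarifying.

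**Conclusion.** The point holds as a small descriptive bias in the comparative-phase AE columns of the Week 96 tables. Control has about 7% to 8% more time at risk in the scenarios examined. Under equal constant hazards it reads about 0.3 to 0.4 points higher at a 48-week risk of 5%, and 1.2 to 1.5 points higher at 20%. The direction favours D/C/F/TAF. No test, error rate or primary result is affected. The unequal windows and the crude incidences come from the SAP text. The sizes rest on assumed AE risks, assumed withdrawal and non-switching shares, a constant hazard and a switch at Week 52. It is worth correcting because existing data suffice.

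**What to change.** Adopt either of the following.

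**A. Common cut for AEs.** In the comparative AE columns only, count control events up to the Week 48 visit (else the projected Week 48 date, with the existing withdrawal rule). Show Week 48 to the switch, on bPI, as a separate control interval. Amend the rule "Last Date of Comparative Treatment Phase +1 day" for control so that the extended phase still begins at first D/C/F/TAF intake; otherwise about four weeks of bPI events would fall in the D/C/F/TAF extension. Cost: an AE-specific cut date, an amended start rule and one extra column. AE tables would then use a different control cut from the concomitant-therapy, worst-grade and vital-sign tables, which should be footnoted.

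**B. Exposure-adjusted rates.** Keep the phases and add incidence rates per 100 subject-years, with person-time for each AE row running to the subject's first event or, if none, to the end of the phase. Do not use total SAP 3.7 duration as the denominator for subjects with an event. Cost: a time-to-first-event derivation for each AE row. This also covers the 44 against 48 week extended columns.

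In either case, as a clarification, state in SAP 2.4 and 5 that the control comparative column includes all treated control subjects, not only those who later switched.

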5.4. Adverse Events

5.4.1. Definitions

Reported AE parameters and grades are based on the Division of AIDS Table for Grading the Severity of Adult and Pediatric Adverse Events ("**DAIDS AE grading table**"). All AEs will be coded using MedDRA version 20.0.

Events of interest

The EOIs groups include a broad list of terms to identify potential cases. The list of all preferred terms belonging to each AEOI group is provided in [Attachment 2](#).

Since many of the terms used to identify potential cases are clinically non-specific, only those retrieved cases that upon medical review are specifically suggestive of /compatible with the AEs of special interest will be commented on in the CSR.

Adverse events of interest (AEOI) groups used for the safety analyses are the following:

- Renal AEOI (for PRT)
Subgroups: laboratory related events,
clinical events
- Bone AEOI (for fractures)
Subgroups: Osteomalacia,
Bone Loss/atrophy,

Fracture, possibly osteoporotic,
Fracture other,
Other Bone Events

- Lipid-related AEOI
- Liver AEOI
- Hyperglycemia AEOI
- Pancreas AEOI
- Severe skin AEOI
- Rash AEOI
- Immune reconstitution inflammatory AEOI
- Coronary artery AEOI
- Ocular AEOI (for posterior uveitis)
- Lipodystrophy AEOI
- Cardiac conduction AEOI
Subgroups: Conduction defects,
Torsade de pointes/QT prolongation
- Convulsion AEOI

Adverse Drug Reaction (ADR)

ADRs will be presented. A list of all ADRs is in the [Attachment 3](#). The medical assessment of the safety data was performed according to a pre-specified algorithm and. In case multiple lists are available (US and EU definitions), ADRs will be tabulated separately per list.

5.4.2. Analysis Methods

A summary will be provided for the following treatment-emergent adverse events:

- any adverse events,
- serious adverse events,
- deaths due to AE,
- adverse events by toxicity grade (as well as AEs with toxicity grade at least 2 and AEs with toxicity grades 3 or 4),
- AEs at least possibly related to study medication,
- AEs for which the medication was temporarily/permanently stopped,
- serious adverse events that were at least possibly related to the medication.

Incidences of AEs for above mentioned analyses will also be presented by SOC and preferred term. There will be no formal statistical testing.

Summary of events and incidence tabulations for individual adverse events will be provided for AEOI and also for ADRs.

AIDS defining illness based on WHO clinical staging will be tabulated.

The number and percentage of subjects who experienced fracture events (subgroups Fracture, possibly osteoporotic and Fracture other of the Bone AEOI for fractures) will be summarized by treatment group.

Selected safety endpoints will be explored by subgroups defined in section 2.7.2. Details for subgroup analyses of safety endpoints will be provided in the DPS.

5.5. Clinical Laboratory Tests

5.5.1. Definitions

Laboratory parameters of the following lab subcategories will be investigated. The results will be displayed grouping the tests as follows:

- General biochemistry:
 - blood: creatine phosphokinase, alpha-1 acid glycoprotein
 - urine/dipstick: blood, nitrite, leukocyte esterase
- Hematology: hematocrit, hemoglobin, platelet count, red blood cell count (RBC), white blood cell count (WBC), mean corpuscular volume (MCV), mean corpuscular hemoglobin (MCH) and mean corpuscular hemoglobin concentration (MCHC)

Hematology differential counts: basophils, eosinophils, lymphocytes, monocytes, neutrophils (counts and %).

Laboratory Events of Interest

- Pancreatic parameters: total amylase, lipase
- Liver related parameters:
 - ALT, AST, alkaline phosphatase (ALP), gamma glutamyl transferase (GGT), bilirubin (all types)
 - Urine/dipstick: bilirubin, urobilinogen
- Lipid parameters: cholesterol, HDL cholesterol (HDL-C) (all types), LDL cholesterol (LDL-C) (all types), TC/HDL, triglycerides; these will be analyzed overall irrespective of fasting status as well as restricted to results from fasting samples separately
- Glucose parameters will be analyzed overall irrespective of fasting status as well as restricted to results from fasting samples separately:
 - blood: glucose
 - urine/dipstick: glucose, ketones
- Renal parameters:
 - blood: total protein, creatinine, blood urea nitrogen, uric acid, phosphorus, potassium, sodium, bicarbonate, chloride, albumin
 - urine/chemistry: creatinine, sodium, phosphate, glucose, urine albumin, urine protein
 - urine/dipstick: glucose, protein

Laboratory toxicities will be derived based on the DAIDS toxicity grading scale (see Protocol).

Note: Local lab results will not be used for the analyses.

5.5.2. Analysis Methods

Descriptive statistics for the actual values and changes from reference will be provided per time point.

Cross-tabulations of the worst toxicity grades through Week 96 versus reference, and cross-tabulations of the worst toxicity grades at Week 96 versus reference will also be provided if applicable. Subject listings of abnormal laboratory values will be provided.

For lipids and renal parameters, within-treatment arm comparison versus reference at Week 96 will be assessed using Wilcoxon signed-rank test.

Additionally, the following lipid-related abnormalities according to NCEP categories will also be tabulated:

- Triglycerides abnormally high (≥ 150 mg/dL)
- Total cholesterol abnormally high (≥ 200 mg/dL)
- LDL abnormally high (≥ 100 mg/dL)
- HDL abnormally low (< 40 mg/dL)

Hy's Law Criteria

In addition, an analysis will be performed to identify all subjects meeting Hy's law criteria i.e. subjects showing 3-fold or greater elevations above the ULN of ALT or AST and a concomitant elevation of serum total bilirubin to $>2 \times \text{ULN}$, without a concomitant elevated serum ALP (defined as serum alkaline phosphatase activity less than $2 \times$ the upper limit of normal).

5.5.3. Creatinine and glomerular filtration

5.5.3.1. Serum Creatinine and Cystatin C

Estimated glomerular filtration rate based on the creatinine clearance will be calculated according to the Cockcroft-Gault formula³ ($\text{eGFR}_{\text{CrCG}}$) and the CKD-EPI formula ($\text{eGFR}_{\text{CrCKD-EPI}}$) and eGFR based on cystatin C clearance will be calculated according to the CKD-EPI formula ($\text{eGFR}_{\text{CystCKD-EPI}}$).

- eGFR_{Cr} according to the Cockcroft-Gault formula (unit: mL/min):

$$\text{Male: } \frac{(140 - \text{age in years}) \times (\text{weight in kg})}{72 \times (\text{serum creatinine in mg/dL})} = \text{eGFR}_{\text{CrCG}} (\text{mL/min})$$

$$\text{Female: } \frac{(140 - \text{age in years}) \times (\text{weight in kg})}{72 \times (\text{serum creatinine in mg/dL})} \times 0.85 = \text{eGFRcr}_{\text{CG}} \text{ (mL/min)}$$

- eGFRcr and eGFRcyst according to the CKD-EPI formula (unit: mL/min/1.73m²):

eGFRcr_{CKD-EPI}

Female: Scr ≤0.7 mg/dL	144 x (Scr/0.7) ^{-0.329} x 0.993 ^{age}
Scr >0.7 mg/dL	144 x (Scr/0.7) ^{-1.209} x 0.993 ^{age}
Male: Scr ≤0.9 mg/dL	141 x (Scr/0.9) ^{-0.411} x 0.993 ^{age}
Scr >0.9 mg/dL	141 x (Scr/0.9) ^{-1.209} x 0.993 ^{age}

eGFRcyst_{CKD-EPI}

Scyst ≤0.8 mg/L	133 x (Scyst/0.8) ^{-0.499} x 0.996 ^{age} [x 0.932 if female]
Scyst >0.8 mg/L	133 x (Scyst/0.8) ^{-1.328} x 0.996 ^{age} [x 0.932 if female]

Scr = serum creatinine (mg/dL), Scyst = serum cystatin C (mg/L)

The changes from reference in serum creatinine, eGFRcr_{CG} and eGFRcr_{CKD-EPI} and eGFRcyst_{CKD-EPI} at Week 96 will be summarized by treatment arm and using descriptive statistics.

Within-treatment arm comparison versus reference at Week 96 will be assessed using Wilcoxon signed-rank test.

Stages of GFR at reference versus the minimum post-reference GFR value and the last available value will be summarized by count and percent of subjects. Kidney disease stages are defined as follows: 1 (Normal): GFR ≥ 90; 2 (Mild): GFR 60-89; 3 (Moderate): GFR 30-59; 4 (Severe): GFR 15-29; 5 (Renal Failure): GFR <15 mL/min).

In addition to the above, the number and proportion of subjects with a >25%, >50% and >75% decrease from reference will be tabulated.

5.5.3.2. Proximal renal tubular function

Proteinuria by Quantitative Assessment

Total urine protein, total urine albumin, urine protein to creatinine ratio (UPCR) and urine albumin to creatinine ratio (UACR) will be summarized by treatment arm and visit using descriptive statistics. The number and proportion of subjects with UACR and UPCR results in the following categories at Week 96 will be tabulates:

- UACR: < 30, 30 to 300, >300 mg/g
- UPCR: < 200 mg/g versus ≥ 200 mg/g

Median (Q1, Q3) percent change from reference over time will be plotted by treatment group.

The evolution over time of total urine protein and total urine albumin will also be presented.

Proteinuria by Urinalysis (Dipstick)

Treatment-emergent proteinuria by urinalysis (dipstick) through Week 96 will be summarized by treatment group. Cross-tabulation of grades at Week 96 versus reference will also be presented.

Other Renal Biomarkers

Selected renal biomarkers retinol binding protein (RBP) and beta-2-microglobulin, RBP to creatinine ratio and beta-2-microglobulin to creatinine ratio will be summarized by treatment arm and visit using descriptive statistics.

The proportions of subjects with beta-2-microglobulin to creatinine ratio ≤ 300 $\mu\text{g/g}$ and $>300\text{mg/g}$ will be tabulated.

The number and proportion of subjects with retinal binding protein to creatinine ratio results in the following categories at Week 96 will be tabulated:

- < 50 years of age (at the time of lab assessment): < 130 mcg/g creatinine, ≥ 130 mcg/g creatinine
- ≥ 50 years of age (at the time of lab assessment): < 172 mcg/g creatinine, ≥ 172 mcg/g creatinine

Phosphate excretion

Other renal biomarkers include urine fractional excretion of phosphate (FEPO4) that will be summarized by treatment arm and visit using descriptive statistics.

Urine fractional excretion of Phosphate (FEPO4) will be calculated as follows:

- Based on unadjusted serum creatinine:
$$\text{FEPO4 (\%)} = (\text{SCr} \times \text{UPO4}) / (\text{SPO4} \times \text{UCr}) \times 100 (\%)$$

The reference, post-reference, and change from reference in FEPO4 will be summarized by treatment arm and visit using descriptive statistics. Median (Q1, Q3) change from baseline in FEPO4 over time will be plotted by treatment group.

Subclinical renal proximal tubulopathy

Potential Markers of Renal Proximal Tubulopathy are

1. Increase in serum creatinine ≥ 0.40 mg/dL from reference.
2. Confirmed ≥ 2 grade level increase from reference in graded proteinuria
3. Confirmed ≥ 1 grade level increase from reference in graded hypophosphatemia
4. Confirmed ≥ 1 grade level increase from reference in graded glycosuria concurrent with serum glucose ≤ 100 mg/dL (normoglycemic glycosuria)

A confirmed laboratory abnormality is defined as an abnormality observed at 2 consecutive post-reference measurements or an abnormality observed at 1 measurement followed by study drug discontinuation

A subclinical renal proximal tubulopathy is defined as confirmed abnormalities in any 2 out of the 4 renal parameters (serum creatinine and one or more of the 3 other markers of tubular dysfunction).

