#### **Renal Biomarkers**

Selected renal biomarkers, including RBP and beta-2-microglobulin, will be summarized by treatment arm and visit using descriptive statistics. The comparison between the 2 treatment arms at Weeks 24 and 48 will be performed using the Van Elteren test stratified for bPI used at screening. The within-treatment comparison will be performed using Wilcoxon signed-rank test.

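### SAP 5.5.3.2 defines the two beta-2-microglobulin/creatinine classes in different units, so ratios above 300 and up to 300,000 µg/g fall in neither class

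*SAP*

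**What the plan says.** Under Other Renal Biomarkers, SAP section 5.5.3.2 plans descriptive statistics by arm and visit for retinol binding protein (RBP), beta-2-microglobulin and their ratios to creatinine. It then adds a two-class table for one of these ratios, which opens "The proportions of subjects with beta-2-microglobulin to creatinine ratio" and sets the limits as follows: "beta-2-microglobulin to creatinine ratio ≤ 300 $\mu\text{g/g}$ and $>300\text{mg/g}$ will be tabulated". The lower class is in micrograms per gram and the upper class in milligrams per gram.

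The other two-class splits in the section each keep to one unit. For RBP to creatinine in subjects under 50 the classes are "< 130 mcg/g creatinine, ≥ 130 mcg/g creatinine"; for subjects aged 50 or over the same form is used with 172 mcg/g. For urine protein to creatinine the SAP has "UPCR: < 200 mg/g versus ≥ 200 mg/g". The urine albumin to creatinine classes (below 30, 30 to 300, above 300) are all in mg/g.

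The protocol gives no cut-off for the beta-2-microglobulin ratio. Its section 11.6 (Renal Biomarkers) says: "Selected renal biomarkers, including RBP and beta-2-microglobulin, will be summarized by treatment arm and visit using descriptive statistics". It follows this with rank-based comparisons between and within arms.

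**The concern.** A split at 300 written with an at-most sign on one side and a greater-than sign on the other reads as a complete division of subjects into not elevated and elevated. With different units it is not complete. A subject just above 300 µg/g is excluded from the lower class and falls far short of the upper one.

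Beta-2-microglobulin matters to the trial's safety question. It is one of the two urine biomarkers that the protocol names, change from baseline in renal biomarkers is a secondary endpoint (protocol 11.1.2), and protocol 1.6 lists beta-2-microglobulinuria among the renal effects to be assessed. This table is the only categorical summary of the marker in the SAP. If it were programmed literally, the elevated cell would miss subjects above 300 µg/g, and no other categorical output would show the omission.

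**Working it through.** **Inputs** (SAP 5.5.3.2): lower class at most 300 µg/g; upper class above 300 mg/g.

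**Conversion.** 1 mg = 1000 µg, so 300 mg/g = 300 × 1000 = 300,000 µg/g.

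**Gap.** The lower class ends at 300 µg/g and the upper class begins above 300,000 µg/g. The ratio of the limits is 300,000 / 300 = 1000, and the width of the gap is 300,000 − 300 = 299,700 µg/g.

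**Classification of test values** chosen to probe the limits (they are not trial data):

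| Ratio (µg/g) | As printed | With µg/g on both sides |
|---|---|---|
| 50 | lower | lower |
| 300 | lower | lower |
| 300.1 | neither | upper |
| 1,000 | neither | upper |
| 30,000 | neither | upper |
| 300,000 | neither | upper |
| 300,001 | upper | upper |

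With one unit, every value falls in exactly one class and the gap is zero. Lower-class membership is the same under both rules; only the upper class changes.

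**Which unit was meant.** Putting either unit on both sides would close the gap, but the two thresholds would differ 1000-fold. Two things point to µg/g: the lower class is already in that unit, and the RBP cut-offs that follow directly are in mcg/g. The section also uses mg/g, for the albumin and protein ratios, and above 300 mg/g is the top albumin class. A carry-over from there is possible, but the documents do not say so. They also do not state the laboratory reporting unit for beta-2-microglobulin.

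**Where the cut-off is used.** It appears only in this table. The subclinical tubulopathy definition in the same section uses serum creatinine, proteinuria, hypophosphatemia and glycosuria. The protocol's renal biomarker analyses use the continuous values. SAP 1.3 states that no formal hypothesis is tested at Week 96.

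**The case against.** The strongest reply is that this is a trivial slip whose meaning is plain. The number is the same on both sides, the signs are complementary, and a programmer would probably query it when the table shell is drawn up. That lowers the practical risk. It does not remove the need to correct the text, because a silent resolution would leave the abnormality threshold undocumented in the plan.

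It can also be said that the mismatch may not exist in the source. The SAP text was extracted from a PDF, and a micro sign misread as m would produce this result. That cannot be ruled out. Against it, the micro sign for the lower class in the same sentence was read correctly.

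Third, little information is lost. The proportion at or below 300 µg/g is still correct, and with subjects who have a value as the denominator, its complement is the proportion above 300 µg/g. The continuous summaries need no cut-off. This stands and limits the severity.

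A reader might go further and infer that essentially no subject would be counted as elevated. The documents give no distribution for this ratio, so they do not support that statement. A reader might also infer that half of the tubular assessment is compromised, since only two urine biomarkers are named. However, SAP 5.5.3.2 also covers the protein and albumin ratios, dipstick proteinuria and fractional excretion of phosphate.

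**Conclusion.** The point holds, at low severity. As printed, the two classes leave a 1000-fold gap: ratios above 300 and up to 300,000 µg/g are in neither class, the upper class is wrong as a definition of elevated, and the two proportions need not sum to 100%. This follows from unit conversion alone and needs no assumption about the data. How many subjects fall in the gap cannot be said from the documents.

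The damage is limited to the upper cell of one descriptive table. It would be wrong to infer any effect on the primary endpoint, sample size, error rate, analysis sets or the tubulopathy definition, because none of them uses this cut-off. The conclusion assumes that the extracted text matches the source SAP. That µg/g was intended on both sides is the most plausible reading, but the documents do not state it.

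**What to change.** First check the sentence in the source SAP and confirm the laboratory reporting unit for the ratio. Then state one unit for both classes: at most 300 and above 300 µg/g creatinine, if the check bears out that reading. Confirm that the programmed table uses the same unit and that the two counts add up to the number of subjects with a value.

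The cost is one character in the SAP and a short check of the program. No new data or further analysis is needed. If the source already reads µg/g on both sides, only the program check remains.
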